9. STATISTICS AND DATA ANALYSIS
10. REGULATORY ISSUES
11. STUDY MANAGEMENT
12. PUBLICATION POLICY
13. REFERENCES

1. GLOSSARY OF ABBREVIATIONS

GDM	Gestational diabetes mellitus
BMI	Body mass index
GI	Glycaemic index
T2DM	Type 2 diabetes mellitus
OGTT	Oral glucose tolerance test
FPG	Fasting plasma glucose
IS	Insulin sensitivity
UCPCR	Urinary C-peptide creatinine ratio
PCOS	Polycystic ovarian syndrome
GAD	Glutamic Acid Decarboxylase

2. KEYWORDS

Gestational diabetes mellitus

Risk factors

Diet

Soluble fibre

Insulin sensitivity

Insulin secretion

Insulin treatment

1. STUDY SUMMARY

TITLE The use of soluble fibre for the prevention of gestational diabetes among high-risk women. A pilot study.

AIMS The primary aim of this study is to evaluate the effect of a soluble fibre supplement in the development of gestational diabetes in women at high-risk. The secondary aim will be to evaluate the effect of the soluble fibre supplement on glycaemic control in high-risk women who develop gestational diabetes in early pregnancy.

DESIGN We plan to conduct a randomised single-blinded controlled study to evaluate the effect of the consumption of soluble fibre, from early to mid-pregnancy, on the incidence of gestational diabetes, insulin sensitivity, insulin secretion and metabolic control in GDM diagnosed participants.

POPULATION We will be studying women with diagnosis of gestational diabetes in previous pregnancies, (considered as high-risk) aged >18 years.

ELIGIBILITY Women over 18 years old with a history of gestational diabetes in previous pregnancies will be eligible to apply to this study. After first assessment, eligible women will be split according to their glycaemic status in women with and without early gestational diabetes.

TREATMENT Participants in the treatment arms will be taking 5 gr of Guar gum fibre supplement with meals three times a day (total daily 15 g). Participants in the placebo arms will be taking 5 gr of Cellulose three times a day (total daily dose 15 g).

DURATION Participants will be involved for 12 weeks.

OUTCOME MEASURES

In women with normal glucose tolerance at first assessment:

Primary outcome: Gestational diabetes (yes/no) at 28 weeks gestation.

Secondary outcomes: Insulin sensitivity and insulin secretion at 28 weeks gestation.

In women with early gestational diabetes (diagnosed at first assessment):

Primary outcome: Glycaemic control assessed the need of insulin treatment (yes/no)

Secondary outcomes: In women requiring insulin treatment: days-to-insulin and total daily insulin dose.

INTRODUCTION

GESTATIONAL DIABETES

Gestational diabetes (GDM), currently defined as diabetes diagnosed in the second or third trimester of pregnancy that is not clearly overt diabetes (1), has been associated with an increased risk of macrosomia and other perinatal complications as well as a higher risk for offspring to develop obesity and type 2 diabetes later in life (2). As for the mothers, women with GDM have a significantly increased risk of developing T2DM in the following years (3). According to the 2015 NICE guidelines for diabetes in pregnancy, approximately 5% of the women given birth in the UK each year have either pre-existing or gestational diabetes. Gestational diabetes accounts for most of the cases of diabetes during pregnancy (87.5%) (4) and its prevalence seems to be on the rise. Previous GDM is a well-established risk factor for developing GDM in subsequent pregnancies, with a recurrence rate of over 40% (5,6). It has been described that women with a history of GDM within the previous 5 years have poorer beta cell compensation and show a faster decline in insulin sensitivity compared to their counterparts without GDM (7). In the UK women with previous GDM should be offered early testing in new pregnancies, either by continuous glucose monitoring or by an oral glucose tolerance test (OGTT) before 16 weeks gestation (4).

GLYCAEMIC INDEX AND HIGH-FIBRE DIET

Glycaemic index is a measure of the impact of carbohydrate-containing foods on post-prandial glycaemic excursions. Both epidemiological and clinical trial evidence supports the beneficial effects of low glycaemic index (GI) diets on glucose homeostasis. Diets that are constructed of low glycaemic index foods with a high dietary fibre content may provide additional metabolic benefits than low glycaemic index diets with a low fibre content. Soluble viscous (gel forming) fibres such as Guar gum, have shown to improve glycaemic control. The consumption of Guar gum before meals has shown to lower postprandial glycaemia in both healthy and diabetic subjects (5-7). As for the long term effects, the consumption of Guar gum supplement showed a decreased in fasting plasma glucose, HbA1c, fasting plasma insulin and HOMA-IR in subjects with metabolic syndrome after 6 months (8) and in patients with type 2 diabetes, 15 gr of Guar gum supplement consumed daily for 48 weeks showed an improvement in postprandial glucose, long-term glycaemic control and C-peptide response after a test meal (9).

The beneficial effects of Guar gum on glycaemic control can possibly be explained through various mechanisms. Firstly, the impact on glycaemic control over the first two hours after consumption of food that possibly relates to the impact of soluble viscous fibres on delaying gastric emptying and slowing the digestion of carbohydrate in the small intestine. There is an additional benefit as Guar gum is fermented by the colonic microbiota to short-chain fatty acids which are recently been shown to have important benefits on beta-cell function presumably by stimulating the production of GLP1 (10).

THE ROLE OF HIGH-FIBRE DIETS IN THE PREVENTION AND TREATMENT OF GESTATIONAL DIABETES

In pregnancy, a high dietary fibre intake has been associated with a lower risk of GDM (11), and in healthy pregnant women, a low GI diet has been associated with lower birth weight and a lower

percentage of large for gestational age newborns (12). As for women who develop GDM, high-fibre diets have been associated with an improvement in perinatal outcomes such as macrosomia (12–14) and risk of C-section (13). In this group of women, high-fibre diets have also to significantly reduce the need to commence insulin treatment (13–15). Despite the documented benefits of a high-fibre diet, as women progress through pregnancy there are often changes in food perception and acceptability which makes compliance to specific diets often difficult. A dietary supplement that can be consumed with meals could be an attractive alternative for complying with the recommended dietary fibre requirements. In pregnancy, Guar gum has shown to reduce postprandial glycaemia after an OGTT (16) and in one study, long term consumption of 10 gr a day showed to decrease both fasting and postprandial glycaemia (17). Therefore, it could be considered in the treatment of women with gestational or who are at high risk of developing the condition.

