5. RANDOMISED CONTROLLED STUDY

Aim: To evaluate the effect of a soluble fibre supplement in glucose metabolism in pregnant women at high risk of developing gestational diabetes.

Study methodology: 12 week randomised, placebo-controlled, single-blinded study.

Intervention: Women will first be categorised according to their glycaemic status into two groups: GDM and glucose tolerant women. Afterwards, each group will be randomised into two groups and given either

- 1) Fibre supplement (Guar gum)
- 2) Placebo (Cellulose)

The participants will take the dietary supplement three times a day for 12 weeks. They will receive regular antenatal control according to NICE guidelines recommendations. Compliance will be addressed by weekly phone calls.

Number of volunteers: The number of participants will be arbitrarily define as no data of this type of intervention exists in this cohort. 40 participants will be recruited. Previous studies, outside pregnancy, have observed metabolic effects in samples of 15-40 subjects.

Recruitment: Women will be recruited in the antenatal clinic at Queen Charlotte and Chelsea's Hospital. An information sheet will be provided to eligible women in the first antenatal visit to explain the purposes of the study. Women who decide to take part will be asked to sign a consent form.

Randomisation: Initially women will be categorised according to glycaemic status in two cohorts: **Glucose tolerant** and **Early gestational diabetes (GDM)** cohort. Each of the two cohorts will then be independently randomised to either intervention or standard care using the sealed envelope website. Guar gum (intervention) and cellulose (placebo) will be provided in identical packed sachets.

STUDY OUTCOME MEASURES

PRIMARY OUTCOME MEASURES

- Glucose values at 0 and 120 minutes during an OGTT performed at 28 weeks in the glucose tolerant group.
- Glycaemic control assessed by need of insulin treatment (yes/no), days to insulin treatment and total insulin dose.

SECONDARY OUTCOME MEASURES

Assessing insulin sensitivity and insulin secretion at 28 weeks of pregnancy in the glucose tolerant cohort of women through validated indices using glucose and insulin (or C-peptide) values derived from the OGTT.

- Insulin sensitivity will be assessed using the Matsuda formula (18).
- Insulin secretion will be assessed by second-void fasting UCPCR as described by McDonald et al (19).

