- Women from the **Glucose tolerant cohort** will undergo a second OGTT. Blood and urine samples will be collected at 0 and 120 minutes. Glycaemic status will then be assessed with the endpoint being the diagnosis of GDM (yes/no). Insulin sensitivity and insulin secretion will be estimated using the same parameters as in the first visit. As part of the study, women will be weight to calculate BMI and gestational weight gain at 28 weeks gestation. The research team will have their last face to face visit with the participant to discontinue the intervention and answer any potential questions about the study.
- In women in the **Early GDM cohort**, glycaemic control will be assessed by the need of insulin treatment (yes/no) and in those requiring insulin the days-to-treatment (insulin) and total insulin dose will be recorded. Data will be obtained by reviewing medical records. As part of the study, women will be weight to calculate BMI and gestational weight gain at 28 weeks gestation. The research team will have their last face to face visit with the participant to discontinue the intervention and answer any potential questions about the study.

PROCEDURES

Women will be advised to fast for 10 hours the night before the oral glucose tolerance test. They will also be advised not to restrict carbohydrate ingestion the three days prior to the OGTT. At the antenatal clinic, blood samples will be collected at baseline (0 min) and at 120 min after the administration of an oral load of 75 g of glucose.

In the baseline sample other parameters will also be determined. Creatinine and HbA1c will measure in all participants and GAD antibodies will be requested in women in whom type 1 diabetes is suspected.

Serum insulin and C-peptide will be collected at 0 and 120 min during the OGTT.

Women will be advised to void their first urine before attending the antenatal clinic. Second-void fasting urine sample will be collected at 0 min during the OGTT. A second urine sample will be collected at 120 min. Urinary C-peptide will measure in these samples will be transfer to boric acid containers, the aliquoted into 1 ml cryotubes and stored at -80 °C until analysis. Serum creatinine will be collected at baseline (0 min) and measure in the central lab. The urinary C-peptide creatinine ratio (UCPCR) will be calculated using these data.

ASSESSMENTS

(i) Gestational diabetes

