Gestational diabetes will be diagnosed if fasting plasma glucose >5.6 mmol/L and/or 120 min plasma glucose >7.8 mmol/L after the glucose load administered in the OGTT. Women with fasting plasma glucose <5.6 mmol/L and 120 min plasma glucose <7.8 mmol/L will be classified as “Glucose tolerant”.

(ii) Insulin sensitivity

Insulin sensitivity will be assessed using the Matsuda index as originally described (18) (Equation 1) and using two modified Matsuda equations in which insulin is substitute by either serum or urinary C-peptide (21,22) (Equations 2 and 3).

Equation 1.

$$\text{ISOGTT} = 10,000 / \sqrt{[\text{FPG} \times \text{fasting insulin}] \times [\text{mean glucose} \times \text{mean insulin during OGTT}]}$$

Equation 2.

$$\text{ISOGTT-} \text{C-pep} = 500,000 / \sqrt{[\text{FPG} \times \text{FsC-pep}] \times [\text{mean glucose} \times \text{mean sC-pep during the OGTT}]}$$

Equation 3.

$$\text{ISOGTT-UCPCR} = 500,000 / \sqrt{[\text{FPG} \times \text{UCPCR}_{\text{pmol}/\text{mmol}}] \times [\text{mean glucose} \times \text{mean UCPCR during the OGTT}]}$$

* FPG= fasting plasma glucose. FsC= fasting serum C-peptide. FUCPCR= fasting urinary C-peptide creatinine ratio.

(iii) Insulin secretion

[figure not shown]
Insulin secretion will be estimated by the UCPCR obtained using the fasting second-void urine sample, as it is strongly correlated with serum insulin, serum C-peptide (19) and 24-h urinary C-peptide (20).

Insulin response will be estimated using the UCPCR calculated with 120 min post-OGTT urine sample, as it is strongly correlated with the C-peptide and insulin area under the curve (19).

(iv) Need of insulin treatment, Days to insulin treatment and Total insulin dose

Medical records of women in the Early GDM cohort will be reviewed in order to determine the need of insulin treatment (yes/no) at 28 weeks gestation. In women requiring insulin treatment at any time during follow up, days-to-insulin treatment, calculated from randomisation day to the day insulin treatment is prescribed, and total insulin dose, calculated as the total dose of insulin international units (IU) divided by weight in Kg (insulin UI/Kg), will be recorded

Timeline for randomised controlled study

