9. STATISTICS AND DATA ANALYSIS

Data handling and analysis will be carried out by SPSS version 20.0 version.

No power calculation to decide sample size will be used. The number of participants has been arbitrarily defined, as it is a pilot study. We aim to recruit 40 women.

Before randomisation, women will be categorised according to their glycaemic status in two cohorts: Glucose tolerant and GDM. Each of these two cohorts will be randomly allocated into the

intervention (soluble fibre supplement) and control (placebo) group. Randomisation will be by sealed envelopes. Participants but not researchers will be blinded as to the type of intervention prescribed.

Differences between group in each cohort will be assessed using Student t test or Mann-Whitney U test for numeric variables depending on distribution; χ^2 will be used for categorical variables.

In the Glucose tolerant women cohort:

For the primary outcome, GDM (yes/no), logistic regression analysis will be performed.

For the secondary outcomes, insulin sensitivity and insulin secretion, linear regression analysis will be performed.

In the early GDM cohort:

For the primary outcome, need for insulin treatment (yes/no), logistic regression analysis will be performed. Additionally days-to-treatment analysis will be performed for those participants starting insulin therapy during follow up.

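### In the early GDM cohort, insulin dose is defined only for women who need insulin, so its comparison between arms is not a randomised one and can dilute, hide or, if mainly low-dose women are spared, reverse a benefit

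*Combined protocol and SAP*

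**What the plan says.** The Study Summary gives the early GDM cohort a yes/no primary outcome, need for insulin, and then "Secondary outcomes: In women requiring insulin treatment: days-to-insulin and total daily insulin dose". Section 6 repeats the restriction twice. At the 4th visit, "in those requiring insulin the days-to-treatment (insulin) and total insulin dose will be recorded". Under Assessments, item (iv), the measures are taken "In women requiring insulin treatment at any time during follow up", with dose "calculated as the total dose of insulin international units (IU) divided by weight in Kg (insulin UI/Kg), will be recorded". No section assigns a value to a woman who never starts insulin.

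Section 5 lists dose among the primary outcome measures and states no restriction: "Glycaemic control assessed by need of insulin treatment (yes/no), days to insulin treatment and total insulin dose". The Study Summary calls it secondary.

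Section 9 has no analysis that names dose. It plans logistic regression for need of insulin and a days-to-treatment analysis limited to women who start insulin. The only line that can cover dose is the general one: "Differences between group in each cohort will be assessed using Student t test or Mann-Whitney U test for numeric variables depending on distribution".

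**The concern.** Need for insulin arises after randomisation and is the cohort's primary outcome. The Introduction says that high-fibre diets reduce the need to start insulin, so the trial's own rationale expects the supplement to change who becomes a user. If it does, the users left in the two arms are no longer comparable by randomisation. A woman spared insulin has the lowest possible dose, and she leaves the dose comparison because of it.

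What is at stake is the reading of the dose result. It would be reported beside the yes/no result as a measure of glycaemic control. It could show little difference, or a higher dose on guar gum, when the insulin requirement of the whole arm has fallen. It would also rest on very few women.

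**Working it through.** The plan has no figure to reproduce: the 40 women are an arbitrary number and no power calculation is used. All rates, doses and cohort sizes below are assumptions, chosen to show direction and rough size.

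**1. Two-group arithmetic.** Let 50% need insulin on placebo and 30% on guar gum. Women who need it either way average 0.50 IU/kg; women whom the supplement spares would have averaged 0.20 IU/kg.

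- Users only, placebo: (0.30 × 0.50 + 0.20 × 0.20) / 0.50 = 0.19 / 0.50 = 0.380. Guar gum: 0.500. Difference +0.120, which looks harmful.
- All women, non-users at zero: placebo 0.190; guar gum 0.30 × 0.50 = 0.150. Difference -0.040, a benefit.

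If the supplement also lowers the dose of the remaining users, the users-only difference is zero when 0.50 × (1 - r) = 0.380, that is, r = 24%. The all-women difference is then 0.30 × 0.380 - 0.190 = -0.076. If spared women would have needed 0.50 IU/kg like the others, the users-only difference is 0.000 and the all-women difference 0.150 - 0.250 = -0.100.

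**2. Selective sparing on a continuous scale.** Severity Z is standard normal. A woman uses insulin if Z exceeds a threshold c, and her dose is 0.2 + 0.2 × (Z - c) IU/kg. The supplement spares the lowest-dose fraction of users and changes nothing else. With 50% of controls on insulin, c = 0 and the mean Z among users is 0.798, so the mean dose is 0.2 + 0.2 × 0.798 = 0.360. Sparing the lowest quarter leaves 37.5% on insulin with mean Z 1.011, so 0.2 + 0.2 × 1.011 = 0.402, a rise of 12%. Over all women the mean goes from 0.50 × 0.360 = 0.180 to 0.375 × 0.402 = 0.151, a fall of 16%.

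| Controls on insulin | Users spared | Users-only mean | All-women mean |
|---|---|---|---|
| 40% | 25% | 0.343 to 0.381 | 0.137 to 0.115 |
| 50% | 25% | 0.360 to 0.402 | 0.180 to 0.151 |
| 60% | 25% | 0.379 to 0.426 | 0.228 to 0.192 |
| 40% | 50% | 0.343 to 0.430 | 0.137 to 0.086 |
| 50% | 50% | 0.360 to 0.454 | 0.180 to 0.114 |
| 60% | 50% | 0.379 to 0.482 | 0.228 to 0.145 |

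The users-only mean rises 11-12% with a quarter spared and 25-27% with half spared. The all-women mean falls about 16% and 36-37%.

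**3. Uniform benefit, same dose model.** Shift every woman's severity down by 0.8 SD, with 50% of controls on insulin. Users on guar gum are then 21.2%. Their mean excess over the threshold is 0.2897 / 0.2119 - 0.8 = 0.567, and their mean dose is 0.2 + 0.2 × 0.567 = 0.313. The users-only mean falls 13% (0.360 to 0.313). The all-women mean falls 63% (0.180 to 0.212 × 0.313 = 0.066). The benefit is diluted, not reversed.

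**4. Numbers of women.** The early GDM share of the 40 is not stated. If it were 20, allocated 10 per arm, the rates in step 1 give about 5 users against 3. The chance of fewer than two users on guar gum is 0.7^10 + 10 × 0.3 × 0.7^9 = 0.028 + 0.121 = 15%.

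**The case against.** The strongest reply is that the trial already asks, in every early GDM woman, whether the supplement reduces the need for insulin. That is the yes/no primary outcome, and Section 9 does not restrict it to users. This stands: women spared insulin are missing from the dose measure (and, by the same restriction, from days to insulin), not from the cohort's main result.

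A reader might infer that a beneficial supplement will show a higher dose among users. The documents do not support that. They say nothing about which women would be spared. Reversal needs mainly low-dose women to be spared with little change in the others' dose; steps 1 and 3 show that it disappears otherwise. Even under selective sparing, a nominally significant harm signal appeared in only about 2-11% of simulated trials.

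A reader might also infer that including the zeros recovers a great deal of power. Against a users-only test it appears to, but the fair comparator is the yes/no analysis already planned. With 10 per arm, 50% of controls on insulin and uniform shifts of 0.8, 1.2 and 1.5 SD, the all-women Mann-Whitney test rejects in about 25, 47 and 60% of simulated trials, and a chi-square test on insulin yes/no in 23, 43 and 57%. Across the assumed insulin rates the gain is about 2-5 points, because the block of zeros drives the rank test.

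Finally, Section 9 never names dose, so a users-only comparison is an inference, and a descriptive users-only summary would be legitimate. But dose is listed as an outcome, in Section 5 as a primary one. With values recorded only in users, the general test has nothing else to compare. That this is a pilot limits the consequence to interpretation; it does not make the comparison valid.

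**Conclusion.** The point holds in a limited form. As written, any between-arm comparison of insulin dose is made in groups selected by a post-randomisation outcome that the supplement is meant to change, so it is not a randomised comparison. That follows from the text and needs no assumption beyond applying Section 9's general test to dose.

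The size of the distortion does rest on assumptions. In the scenarios examined it runs from dilution (a 13% fall among users against 63% over all women), through no visible difference, to a reversed sign (users-only up 11-12% against an all-women fall of about 16%). These are illustrations, not estimates for this trial. The primary yes/no analysis is unaffected. The change is worth making because dose is a named outcome and the correction is nearly free.

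**What to change.** - In the Study Summary and in Section 6 (4th visit and Assessments (iv)), define the dose outcome for all randomised early GDM women, with 0 IU/kg for a woman not on insulin.
- Use one dose definition throughout. The Study Summary has a daily dose; Section 6 has total units divided by weight, with no time unit.
- Use one time basis. Assessments (iv) takes need for insulin as at 28 weeks but dose in women treated at any point in follow-up. State which applies, so that it is settled whether a woman who starts and later stops insulin scores zero.
- Make the outcome primary or secondary, the same in Section 5 and the Study Summary.
- In Section 9, compare the arms over all randomised early GDM women with the Mann-Whitney test already named, corrected for ties. Report dose among users only as a description, labelled as not a randomised comparison.

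The cost is wording. Section 6 already has the records of early GDM women reviewed for insulin need, so no new data, visits or participants are required. The downside is small: with many zeros the mean is harder to interpret and the rank test largely follows the yes/no outcome. The gain is a dose result that is valid and consistent with the primary outcome, not much extra power.
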